DATE: HH:MM/DDMMMYYYY

Programming Note:

• Repeat for 14.2.2.7.13 Proportion of Subjects with ≥4 Point Improvement in AI-NRS from Baseline to Week 4 – LOCF for mITT Population

• Add new footnote "Note: LOCF = Last Observation Carried Forward." as the first footnote.

Footnote [1] will be same as in 14.2.2.5.13, except changing "WI-NRS" to "AI-NRS"

Protocol: PRB244-01 Confidential

ADDENDUM TO SAP v3.0

Version 1.0 22-Apr-22

Table 14.2.2.10.2a Mean Change in EASI Total Score from Baseline to Weeks 2, 4, and 8 – WOCF (mITT Population)

| Visit | Statistic Type | Statistic | B244 O.D. 5.0 (N=xx) | B244 O.D. 20.0 (N=xx) | Pooled B244 (N=xx) | Vehicle (N=xx) |
|--------------------------|----------------|--|---|---|---|-------------------------------------|
| Week 2 CFB [1] | MMRM [2,3] | n LSM (SE) [4] 95% CI | xx xx.x (xx.xxx) (xx.x, xx.x) | xx xx.x (xx.xxx) (xx.x, xx.x) | xx xx.x (xx.xxx) (xx.x, xx.x) | xx xx.x (xx.xxx) (xx.x, xx.x) |
| | v. Vehicle | LSM Difference (SE) 95% CI p-value | xx.x (xx.xxx) (xx.x, xx.x) x.xxxx | xx.x (xx.xxx) (xx.x, xx.x) x.xxxx | xx.x (xx.xxx) (xx.x, xx.x) x.xxxx | N/A N/A N/A |
| Repeat for Weeks 4 and 8 | 20.0 v 5.0 | LSM Difference (SE) 95% CI p-value | N/A N/A N/A | xx.x (xx.xxx) (xx.x, xx.x) x.xxxx | N/A N/A N/A | N/A N/A N/A |

Note: WOCF = Worst Observation Carried Forward.

[1] CFB = Change from Baseline.

[2] MMRM = Mixed Model with Repeated Measures.

[3] Model uses a compound symmetry covariance structure and contains visit, treatment group, visit-by-treatment interaction, and baseline EASI total score as explanatory variables. All subjects who meet mITT criteria are included. Data collected from the week of first on-treatment rescue medication use through the end of the study and missing data due to subject dropout will be imputed using WOCF. Data collected prior to the week of first on-treatment rescue medication use or dropout will be included.

[4] LSM = Least Squares Mean. SE = Standard Error.

Source: Listing XXXX

PROGRAM NAME: XXXXXXXXXX

Programming Note:

- Repeat for 14.2.2.10.5 Mean Change in EASI Total Score from Baseline to Week 4 LOCF for ITT Population
 - First column will contain only "Week 4 CFB [1]"
 - Add new footnote "Note: LOCF = Last Observation Carried Forward." as the first footnote.
 - Footnote [3] will be "Model uses a compound symmetry covariance structure and contains treatment group and baseline EASI total score as explanatory variables. All subjects who meet ITT criteria are included and no data is excluded based on rescue medication use. Any values missing at Week 4 will be imputed using LOCF."
- Repeat for 14.2.2.11.2a Mean Change in IGA from Baseline to Weeks 2, 4, and 8 WOCF for mITT Population
 - Footnote [3] will be same as in 14.2.2.10.2a, except changing "EASI" to "IGA"

DATE: HH:MM/DDMMMYYYY

Protocol: PRB244-01 Confidential

ADDENDUM TO SAP v3.0

Version 1.0 22-Apr-22

- Repeat for 14.2.2.10.5 Mean Change in IGA from Baseline to Week 4 LOCF for ITT Population
 - First column will contain only "Week 4 CFB [1]"
 - Add new footnote "Note: LOCF = Last Observation Carried Forward." as the first footnote.
 - Footnote [3] will be same as in 14.2.2.10.5, except changing "EASI" to "IGA"

Protocol: PRB244-01 Confidential

ADDENDUM TO SAP v3.0

Version 1.0 22-Apr-22

Table 14.2.2.14.7 Proportion of Subjects with \geq 75% Improvement in EASI (EASI-75) from Baseline to Week 4 – LOCF (ITT Population)

| | | | B244 O.D. 5.0 | B244 O.D. 20.0 | Pooled B244 | Vehicle |
|--------|----------------|------------------------|-------------------|-------------------|-------------------|--------------|
| Visit | Statistic Type | Statistic | (N=xx) | (N=xx) | (N=xx) | (N=xx) |
| Week 4 | Logistic [1,2] | n/N (Proportion %) [3] | xx/xx (xx.x) | xx/xx (xx.x) | xx/xx (xx.x) | xx/xx (xx.x) |
| | | 95% CI | (xx.x, xx.x) | (xx.x, xx.x) | (xx.x, xx.x) | (xx.x, xx.x) |
| | v. Vehicle | Odds Ratio (95% CI) | x.xx (x.xx, x.xx) | x.xx (x.xx, x.xx) | x.xx (x.xx, x.xx) | N/A |
| | | p-value | X.XXXX | X.XXXX | X.XXXX | N/A |
| | 20.0 v 5.0 | Odds Ratio (95% CI) | N/A | x.xx (x.xx, x.xx) | N/A | N/A |
| | | p-value | N/A | X.XXXX | N/A | N/A |

Note: LOCF = Last Observation Carried Forward.

[1] Logistic regression model contains treatment group as the explanatory variable. All subjects who meet ITT criteria are included and no data is excluded based on rescue medication use. Any values missing at Week 4 will be imputed using LOCF.

[2] Treatment response is improvement by \geq 75% in EASI score.

[3] n is the number of subjects who have improved at that visit. N is the number of subjects with data at that visit, regardless of improvement status.

Source: Listing XXXX

PROGRAM NAME: XXXXXXXXXX

DATE: HH:MM/DDMMMYYYY

Programming Note:

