3.2.2 Efficacy - Secondary Endpoints

The secondary efficacy endpoints are:

- Proportion of subjects with \geq 4point improvement in WI-NRS from Baseline to Week 4
- Proportion of subjects with any improvement in WI-NRS from Baseline to Week 4
- Mean change (absolute and percent) in AI-NRS from Baseline to Week 4
- Proportion of subjects with \geq 4 point improvement in AI-NRS from Baseline to Week 4
- Proportion of subjects with any improvement in AI-NRS from Baseline to Week 4
- Mean change (absolute and percent) in WI-NRS from Baseline to Week 2
- Proportion of subjects with \geq 4 point improvement in WI-NRS from Baseline to Week 2
- Mean change (absolute and percent) in POEM from Baseline to Week 4
- Mean change (absolute and percent) in 5-D Pruritus Scale from Baseline to Week 4

The endpoints will be reported for all weeks or all visits. The primary endpoint of mean change in WI-NRS is also presented at all weeks for both absolute and percent change. Absolute change will be considered the primary endpoint with percent change as supportive. Any improvement in WI-NRS and AI-NRS is defined as ≥ 1 point improvement from Baseline.

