7.4 Efficacy Analysis

All efficacy analyses will be performed on the mITT population and PP population using the methods described below. Regression models will include all eligible subjects for the respective analysis, from the 3 treatment arms.

- *Primary Analysis*: Includes data for all subjects in the respective population (mITT/PP)
- *Sub-Analysis*: Excludes data collected on/after date of first on-treatment rescue medication use through the end of the study.
 - For WI-NRS/AI-NRS endpoints, excludes data from *week* of first on-treatment rescue medication use.
- *Non-Responder Imputation (NRI) Analysis*: Subjects who discontinue treatment early or who take on-treatment rescue medications will be imputed as a non-responder for assessments that occur on/after date of discontinuation/on-treatment rescue medication use through the end of the study.

STATISTICAL ANALYSIS PLAN

Version 3.0 12-Jan-22

- For WI-NRS/AI-NRS endpoints, excludes data from *week* of discontinuation/first on-treatment rescue medication use.
- Subjects who discontinue early should have at least one treatment-emergent adverse event (TEAE) leading to discontinuation in order to have their data imputed for NRI analysis.

| Efficacy Analyses | lyses | A | cacy | Effi |
|-------------------|-------|---|------|------|
|-------------------|-------|---|------|------|

| Measure | Endpoints | Analysis |
|--------------------|---|--|
| WI-NRS/ AI-NRS* | Mean Change from Baseline | Primary Primary/Sensitivity Sub-Analysis Sub-Analysis/Sensitivity |
| WI-NRS/ | Improvement | Primary Primary/Sensitivity Sub-Analysis Sub-Analysis/Sensitivity NRI NRI |
| AI-NKS* | (4-Point, Any) | 6. NRI/Sensitivity |
| 5D | Mean Change from Baseline | 2. Sub-Analysis |
| EASI | Mean Change from Baseline | Primary Sub-Analysis |
| EASI | Improvement (≥50%, ≥75%, ≥90%) | 1. Primary 2. Sub-Analysis 3. NRI |
| IGA | Mean Change from Baseline | 1. Primary 2. Sub-Analysis |
| IGA | Improvement (2-Point to Clear/Almost Clear, Clear/Almost Clear, Any) | Primary Sub-Analysis NRI |
| POEM | Mean Change from Baseline | Primary Sub-Analysis |

*WI-NRS/AI-NRS analyses require at least 1 diary entry per week to calculate the weekly average, except for the sensitivity analyses, where at least 4 diary entries per week are required.

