A Phase II, Randomized, Double-Blind, Vehicle Controlled Study of the Efficacy, Safety, and Tolerability of B244 Topical Spray for the Treatment of Pruritus in Adults with a History of Atopic Dermatitis

Sponsor:

AOBiome, LLC [name]

ADDENDUM TO SAP v3.0

Version 1.0 22-Apr-22

ADDENDUM TO SAP REVIEW AND APPROVAL

This Addendum to Statistical Analysis Plan v3.0 (12Jan2022) has been prepared in accordance with team reviewers' specifications.

| Prepared by: [name]. Signing Reason: 1 am the author of this document Signing Time: 03 May 2022 4:44:40 AM PDT F18BA 1C2EF7C48A4B775BE54652AC840 | 03 May 2022 |
|--|------------------|
| [name], Bio-Statistician | Date |
| Sponsor Review: | 05 May 2022 |
| [name], Bio-Statistician | Date 05 May 2022 |
| [name], VP of Clinical Operations | Date |

ADDENDUM TO SAP v3.0

Version 1.0 22-Apr-22

Table of Contents

| 1 | Background and Purpose | . 4 |
|---|--|-----|
| 2 | Request 1: Worst Case Analysis | . 4 |
| 3 | Request 2: Intention-to-Treat Analysis | . 5 |
| 4 | List of Tables | . 6 |
| 5 | Table Shells | . 8 |

ADDENDUM TO SAP v3.0

Version 1.0 22-Apr-22

1 Background and Purpose

The purpose of this addendum to the final Statistical Analysis Plan (SAP) for the PRB244-01 study (v3.0 dated 12Jan2022) is to describe additional statistical analyses that will be performed in order to address requests by the FDA made on 27Mar2022. These requests are detailed in the sections below.

2 Request 1: Worst Case Analysis

FDA Request: You proposed the non-responder imputation analysis in which subjects who discontinue treatment early or who take on-treatment rescue medications will be imputed as a non-responder. Similar to the non-responder imputation analysis, we recommend that you provide additional analyses on the primary efficacy endpoint and relevant efficacy endpoints in which the underlying score-based variable values (e.g., WI-NRS, AI-NRS, IGA, etc.), are imputed with the worst score on/after date of first rescue medication use through the end of the study.

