As a parallel to the non-responder imputation analysis, for score-based endpoints of WI-NRS, AI-NRS, IGA, and EASI, we will perform worst-value imputation on/after the date of first ontreatment rescue medication or date of subject early discontinuation through the end of the study. For this sensitivity analysis, all values on/after the date of first on-treatment rescue medication use or all values missing due to subject early discontinuation will be replaced with the worst value observed for each subject between first post-baseline assessment and first use of ontreatment rescue medication (WOCF). In the event there is no observation after baseline recorded, WOCF will be Baseline values.

Subjects who discontinue early should have (1) at least one treatment-emergent adverse event (TEAE) leading to discontinuation and (2) discontinuation occurring prior to their Week 4 visit in order to have their data imputed for WOCF analysis.

In cases where subjects completed the treatment period, but did not complete all of the follow-up period, the following logic will be used in order to fully parallel the NRI analysis. If subjects use rescue medications while on treatment and discontinue after the Week 4 visit, then only values from first on-treatment rescue medication use through last attended visit will be imputed with WOCF (i.e., missing data from visits that did not occur after Week 4 would not be imputed in this case).

The mITT population will be used for this analysis. For WOCF imputation of WI-NRS and AI-NRS values, the worst-observation would be the highest weekly average (not highest daily score) reported after baseline and before first on-treatment rescue medication use or before subject early discontinuation.

ADDENDUM TO SAP v3.0

Version 1.0 22-Apr-22

If a situation occurs where a visit is missed but a subsequent visit takes place for the same subject, then the missing data for that interim visit will not be imputed unless that visit occurs on/after the date of first on-treatment medication use.

3 Request 2: Intention-to-Treat Analysis

FDA Request: We recommend that you perform additional sensitivity analyses to include dropouts for whom no single score is collected and thus missing data handling strategies are to be considered. In this analysis, the analysis population will be the intent-to-treat (ITT) population.

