To approximate an intent-to-treat population, LOCF methods will be applied for all randomized subjects missing Week 4 responses for endpoints (WI-NRS, AI-NRS, IGA, EASI, and responder analyses). Subjects missing Week 4 values will have their measurement imputed to be the LOCF value on treatment or baseline, whichever is later. Sensitivity analysis of WI-NRS, AI-NRS, IGA, EASI, and related responder analyses will be performed.

Intention-to-Treat Population (ITT): All subjects who were randomized, regardless of exposure to treatment.

For subjects who were randomized, but did not receive treatment, the baseline WI-NRS and AI-NRS scores will be calculated using the same approach that is used for treated subjects (as described in section 6.4 of the SAP), except that the reference date will be the date of the baseline visit instead of the date of first dose.

ADDENDUM TO SAP v3.0

Version 1.0 22-Apr-22

4 List of Tables

| Display Number | Title | Population | Unique/ | Request |
|----------------|---|------------|---------|---------|
| | | | Repeat | # |
| 14.2.2.2a | Mean Change in WI-NRS from Baseline to Week 4 – ANCOVA - WOCF | mITT | Repeat | 1 |
| 14.2.2.2b | Mean Change in WI-NRS from Baseline to Week 4 – ANCOVA – WOCF Sensitivity | mITT | Repeat | 1 |
| 14.2.2.2c | Mean Change in WI-NRS from Baseline to Week 4 – ANCOVA - LOCF | ITT | Repeat | 2 |
| 14.2.2.3.4a | Mean Change in WI-NRS from Baseline to Weeks 1 Through 8 - WOCF | mITT | Repeat | 1 |
| 14.2.2.3.4b | Mean Change in WI-NRS from Baseline to Weeks 1 Through 8 - WOCF Sensitivity | mITT | Repeat | 1 |
| 14.2.2.4.4a | Mean Change in AI-NRS from Baseline to Weeks 1 Through 8 - WOCF | mITT | Repeat | 1 |
| 14.2.2.4.4b | Mean Change in AI-NRS from Baseline to Weeks 1 Through 8 - WOCF Sensitivity | mITT | Repeat | 1 |
| 14.2.2.4.9 | Mean Change in AI-NRS from Baseline to Week 4 - LOCF | ITT | Repeat | 2 |
| 14.2.2.5.13 | Proportion of Subjects with ≥4 Point Improvement in WI-NRS from Baseline to Week 4 - LOCF | ITT | Repeat | 2 |
| 14.2.2.7.13 | Proportion of Subjects with ≥4 Point Improvement in AI-NRS from Baseline to Week 4 - LOCF | ITT | Repeat | 2 |
| 14.2.2.10.2a | Mean Change in EASI Total Score from Baseline to Weeks 2, 4, and 8 - WOCF | mITT | Repeat | 1 |
| 14.2.2.10.5 | Mean Change in EASI Total Score from Baseline to Week 4 - LOCF | ITT | Repeat | 2 |
| 14.2.2.11.2a | Mean Change in IGA from Baseline to Weeks 2, 4, and 8 - WOCF | mITT | Repeat | 1 |

ADDENDUM TO SAP v3.0

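### The worst-case (WOCF) imputation has no baseline floor, so a rescued subject can enter the mean-change sensitivity tables as improved

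*SAP*

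**What the plan says.** The Addendum to SAP v3.0, Section 2, answers an FDA request that underlying scores "are imputed with the worst score on/after date of first rescue medication use through the end of the study". The section is titled Worst Case Analysis and opens by presenting itself as a counterpart of the non-responder imputation (NRI) analysis.

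The replacement value is the "worst value observed for each subject between first post-baseline assessment and first use of ontreatment rescue medication (WOCF"). For the two itch scales, "the worst-observation would be the highest weekly average (not highest daily score) reported after baseline and before first on-treatment rescue medication use". Baseline has one role: "In the event there is no observation after baseline recorded, WOCF will be Baseline values". The same approach covers values missing after a discontinuation that was caused by a TEAE and occurred before Week 4.

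Addendum Section 4 lists eight WOCF tables, all of mean change: 14.2.2.2a and 14.2.2.2b (WI-NRS Week 4 ANCOVA), 14.2.2.3.4a and b (WI-NRS by week), 14.2.2.4.4a and b (AI-NRS by week), 14.2.2.10.2a (EASI) and 14.2.2.11.2a (IGA). The first is titled "Mean Change in WI-NRS from Baseline to Week 4 – ANCOVA - WOCF". The WOCF footnotes in Section 5 add no floor at baseline.

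Under NRI (SAP Section 7.4), subjects "who take on-treatment rescue medications will be imputed as a non-responder for assessments that occur on/after date of discontinuation/on-treatment rescue medication use".

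**The concern.** The window for the worst value opens after baseline. If every retained score before rescue is better than baseline, the worst of them is still an improvement, and it is carried to Week 4 and beyond. A worst-case table then credits a subject who needed rescue with benefit. This does not fit the section's title or its stated aim of mirroring NRI, which gives such a subject no credit from rescue onward.

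The rule is also uneven. A WI-NRS subject rescued in Week 1 has no earlier weekly average and, if the fallback is applied, gets a change of zero. A subject rescued in Week 3 after two good weeks keeps the early gain.

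At stake is how the WOCF tables can be read as a stress test of the primary result. The primary ANCOVA itself keeps data after rescue and does not use WOCF.

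**Working it through.** **The rule, followed literally.** Imputed value = max(post-baseline values before rescue), or baseline if there are none. With a floor: max(baseline, post-baseline values before rescue). The plan gives no figure for this rule, so there is none to reproduce.

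**IGA, by hand.** Baseline 3, Week 2 = 2, first rescue a few days before the Week 4 visit, Week 4 = 3.
- As written: 2 - 3 = -1.
- Observed: 3 - 3 = 0.
- With floor: max(3, 2) - 3 = 0.

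On scheduled visits, Week 2 is the only IGA or EASI value available to a subject rescued between Weeks 2 and 4, so one good visit fixes the imputed value.

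**WI-NRS, by hand.** Baseline 8.5; Weeks 1-4 = 6.0, 5.5, 9.0 (rescue week), 8.0.
- As written: 6.0 - 8.5 = -2.5.
- Observed: 8.0 - 8.5 = -0.5.
- With floor: 8.5 - 8.5 = 0.

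Here part of the gap arises because the rescue week is also dropped. Had Week 3 counted, the imputed change would be 9.0 - 8.5 = +0.5.

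**Size, WI-NRS only.** From the documents: SD 2.5 and difference 0.65 (SAP Section 7.1), and washout weekly averages of at least 6 (Protocol Section 6.2). The documents give no rescue rate, no trajectory and no link between itch and rescue, so everything else is assumed:
- baseline normal, mean 8, SD 0.9, clipped to 6-10;
- vehicle mean change -0.9, -1.5, -1.9, -2.2 at Weeks 1-4;
- B244 a further -0.26, -0.455, -0.585, -0.65;
- SD 1.75, 2.125, 2.375, 2.5; week-to-week correlation 0.70 or 0.85;
- rescue either rising with itch (log-odds 0.8 per point) or unrelated to it.

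The wider column also covers runs with the vehicle trajectory scaled by 0.3 to 1.5.

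| Share of rescued subjects | Base trajectory | Wider runs |
|---|---|---|
| Below baseline, itch-driven | 21-29% | about 20-33% |
| Below baseline, unrelated | 48-51% | about 36-56% |
| At least 1 point below, itch-driven | 9-15% | about 8-20% |
| At least 1 point below, unrelated | 32-35% | about 21-41% |

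**Effect of the floor on the Week 4 contrast** (B244 minus vehicle; negative favours B244). Before covariate adjustment, shift = p_active × c_active - p_vehicle × c_vehicle, where p is the rescue rate and c the mean rise per rescued subject from adding the floor. For unrelated rescue at correlation 0.70:
- 30% in both arms: 0.30 × 0.901 - 0.30 × 0.752 = +0.045.
- 30% vehicle, 20% active: 0.20 × 0.919 - 0.30 × 0.752 = -0.042.
- 20% vehicle, 30% active: 0.30 × 0.901 - 0.20 × 0.760 = +0.118.

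Over the wider runs, the shift is about 0.05 or less at equal or near-equal rates. At 30%/20% (vehicle/active) the B244 effect grows by about 0.02-0.07; at 20%/30% it shrinks by about 0.04-0.14. The design standard error is 2.5 × √(2/160) = 0.28, so 0.05 is about 0.18 of it.

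**Average behaviour.** With unrelated rescue at 30% in both arms and correlation 0.70, mean change in rescued subjects is -0.59 as written and +0.23 with the floor. The assumed mean observed change, before clipping, is (-2.2 - 2.85)/2 = -2.53. On average the written rule is thus already harsher than the observed data; the defect lies in individual subjects.

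**The case against.** The rule is explicit: it names a recognised method, defines its window twice and gives baseline a stated role. The quoted FDA request does not say whether the worst score means worst observed or worst possible, or whether baseline counts. It therefore cannot be shown from the documents that the request is unmet, and a baseline floor is one reasonable reading among several. That stands. The point is measured only against the section's own title and opening aim.

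Three stronger readings are tempting and are not supported.
- The phrase "the following logic will be used in order to fully parallel the NRI analysis" might be taken as the standard for the imputed value. It concerns subjects who finish treatment but not follow-up, and settles only which follow-up visits are imputed.
- The WOCF and NRI tables might seem to contradict each other, because "Any improvement in WI-NRS and AI-NRS is defined as ≥ 1 point improvement from Baseline" and some imputed changes pass that mark. The plan never applies a responder threshold to WOCF values: NRI feeds proportions and WOCF feeds means.
- The rule might be thought to favour B244. It has no fixed direction; if more vehicle than B244 subjects are rescued, the floor makes B244 look better.

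It is also fair that the shift is small, that larger shifts need unequal rescue rates, and that the AI-NRS, EASI, IGA and by-week tables were not modelled.

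**Conclusion.** The point holds, with low severity. As written, the worst-case rule can enter a rescued subject as improved, sometimes by more than was observed, in eight sensitivity tables. The IGA example shows this exactly and needs no assumption. The percentages and contrast shifts are illustrative, apply to WI-NRS only, rest on assumed rescue rates and trajectories, and are not bounds. The definitive primary ANCOVA and all responder tables are unaffected.

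**What to change.** In Addendum Section 2, define the imputed value as the worse of baseline and all post-baseline values before first on-treatment rescue (or before discontinuation). This also settles the subject with no post-baseline value before rescue but some after it, whom the present fallback wording does not clearly cover. Amend the footnotes of the eight WOCF tables to match, and print the number rescued by arm beside each, because the direction of the shift depends on it.

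The cost is two sentences, one derivation and the footnotes. Mean change in rescued subjects becomes less favourable, by about 0.2 to 0.9 points on the base assumptions, and the between-arm contrast may move either way. Rescue treatment itself is not touched.

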4 STUDY DESIGN

4.1 General Study Design and Plan

This is a prospective, vehicle-controlled, double-blind, multicenter, randomized phase II trial, comparing the effect of twice daily B244 applications for 4 weeks vs vehicle applications on treatment of mild to moderate pruritus associated with atopic dermatitis.

Approximately 576 subjects are planned to be enrolled.

The total duration of the study will be approximately 11 weeks. Participants will report for a Screening visit and if all inclusion/exclusion criteria are met, subjects will go through a two-week washout phase before reporting for a Baseline visit.

After Screening and Baseline, participants will be randomized to one of two doses of B244 or vehicle application for 4 weeks.

Randomization will be 1:1:1 so that an equal number of patients will be treated in each arm of the study.

STATISTICAL ANALYSIS PLAN

Version 3.0 12-Jan-22

All B244 randomized subjects will be treated at the dose of 1×10^{10} cells/ml (O.D. 5.0) or 4×10^{10} cells/ml (O.D. 20.0).

Subjects must be willing and able to complete diary within a consistent time frame on a daily basis and to comply with restrictions on allowable therapies for the duration of the study.

All subjects will attend a Screening visit not more than 21 days prior to Baseline (Day 0).

Subjects will be required to return to the clinic at Baseline, Day 14 (Week 2) and Day 28 (Week 4) visits. All subjects will be asked to attend a Week 8 follow-up visit 4 weeks (28 (± 3) days) after the last dose of study medication.

Subjects will apply a total of 10 pumps of IP per application across all affected areas twice-a-day (i.e., 10 pumps in the morning and 10 pumps again at night) for 4 weeks.

Safety evaluations will consist of review of participant's medical history at screening and ongoing assessment of adverse events reported throughout the study duration.

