7 STATISTICAL ANALYSES

7.1 Sample Size Determination

Approximately 576 subjects may be enrolled to account for 16.7% drop out rate prior to completing the study. A total of 160 evaluable subjects per group (480 total) are required to achieve at least 80% power to detect a pairwise difference of 0.65 in mean WI-NRS change from Baseline to Week 4 between one of two active doses of B244 and vehicle control when assuming a standard deviation of 2.5 and applying a Dunnett Testing Method at a one-sided familywise error rate of 0.10.

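### The only all-randomised sensitivity analysis fills missing Week 4 values by LOCF and treats them as observed, so it is not a sound check on the effect of dropout

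*SAP*

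**What the plan says.** SAP v3.0 analyses efficacy in the mITT and per-protocol populations. Section 7.2.4 limits mITT to randomised subjects who were dosed and had a clinic evaluation after baseline. Section 7.6 imputes no efficacy scores beyond the weekly-average rule for diaries.

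The Addendum to SAP v3.0 (22 April 2022) responds to two FDA requests. In the second (Addendum Section 3), the FDA asks for further sensitivity analyses in the ITT population that bring in dropouts with no score, and leaves the method open: "thus missing data handling strategies are to be considered". The sponsor's answer is that "LOCF methods will be applied for all randomized subjects missing Week 4 responses for endpoints" (WI-NRS, AI-NRS, IGA, EASI and their responder versions). The value carried forward is the later of the last on-treatment value and baseline. ITT here means everyone randomised, treated or not. The footnote for the WI-NRS LOCF table puts the filled values into the same ANCOVA and one-sided Dunnett procedure as the primary analysis and adds nothing for imputation.

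No other planned analysis uses the all-randomised set. The worst-observation analysis (Addendum Section 2) is confined to mITT, and the non-responder analysis (SAP Section 7.4) to mITT and per-protocol. In both, a dropout who used no rescue is imputed only if an adverse event led to the discontinuation.

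**The concern.** LOCF holds a dropout at an early score. If scores in all arms keep improving up to Week 4, each carried-forward value understates the improvement that subject would have been credited with, and the arm that loses more subjects is penalised more. Improvement in every arm is plausible here, though neither document states it: Protocol Section 6.2 requires WI-NRS of 7 or more at Screening and Baseline and weekly averages of 6 or more in washout, and selection on high scores invites regression to the mean.

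The subjects at issue include those who leave without an adverse event and without rescue use, for example for lack of effect or loss to follow-up. Among the planned analyses that impute, only LOCF fills their Week 4 score. A check whose bias changes sign with an unknown dropout pattern cannot tell the regulator whether the primary result survives the missing data.

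**Working it through.** **Inputs from SAP Section 7.1.** "A total of 160 evaluable subjects per group (480 total) are required"; "assuming a standard deviation of 2.5"; difference 0.65; "applying a Dunnett Testing Method at a one-sided familywise error rate of 0.10"; "Approximately 576 subjects may be enrolled to account for 16.7% drop out rate prior to completing the study". Allocation is 1:1:1 (Section 4.1), so 192 are randomised per arm.

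**Plan's own figures.** 1 - 480/576 = 16.7%, as stated. The one-sided Dunnett critical value for two doses against vehicle (correlation 0.5) is 1.577. At 160 per arm, SE = 2.5 × √(2/160) = 0.2795, and power to reject for at least one of two active doses is 89.5%, consistent with the stated minimum of 80%.

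**Assumptions not in the documents.** Each arm improves linearly by A points by Week 4. Dropout is random within arm. A quarter of dropouts have baseline only; the rest stop equally often after Week 1, 2 or 3. Weekly SDs are 1.6, 2.0, 2.3 and 2.5, with correlation 0.7.

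**Bias in closed form.** A dropout's carried-forward value contains on average 0.25 × 0 + 0.25 × (0.25 + 0.50 + 0.75) = 0.375 of the full improvement, so it falls short by 0.625 × A. With dropout dV on vehicle and dB on B244 and no true effect:

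LOCF difference (B244 minus vehicle; negative favours B244) = 0.625 × A × (dB - dV)

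The chance of a false positive on either dose follows by shifting the Dunnett statistic by this bias divided by the simulated LOCF SE (0.245, 0.249 and 0.256 for A = 1, 2, 3).

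| Dropout, vehicle / B244 | A | Bias | Either-dose false positive (nominal 10%) |
|---|---|---|---|
| 16.7% / 16.7% | any | 0 | 10% |
| 20% / 15% | 2 | -0.06 | 16% |
| 25% / 12.5% | 1 | -0.08 | 17% |
| 25% / 12.5% | 2 | -0.16 | 27% |
| 25% / 12.5% | 3 | -0.23 | 39% |
| 10% / 20% | 2 | +0.13 | 3.5% |

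Simulation at 192 per arm agrees: for A = 2, bias -0.157 and 27% at 25% / 12.5%, and +0.119 and 3.9% at 10% / 20%. The comparison of observed Week 4 values stayed at 9-11% throughout.

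**True effect of 0.65.** With equal 16.7% dropout, LOCF gives 0.65 × (1 - 0.625 × 0.167) = 0.58. At 25% / 12.5% with A = 2 it gives -2.65 × (1 - 0.625 × 0.125) + 2 × (1 - 0.625 × 0.25) = -0.76 (simulated -0.75). At 10% / 20% the simulated estimate is -0.45.

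**Standard error.** Counting 192 rather than 160 per arm as observed cuts the SE from 0.2795 to 2.5 × √(2/192) = 0.2552, a fall of 8.7%. Against multiple imputation under missing-at-random, LOCF SEs were 7-11% smaller in one set of simulations (0.249 against 0.272 at equal dropout) and 5% smaller in another (0.254 against 0.268).

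**Comparator methods.** In 600 simulated trials with A = 2, 25% / 12.5% dropout and no true effect, either-dose false positives were 30% for LOCF, 12% for missing-at-random multiple imputation and 9% for imputation from the vehicle arm. With a true difference of -0.65 the estimates were -0.74, -0.63 and -0.58.

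**The case against.** **No claim of success rests on this table.** SAP Section 7.2.6 gives the decisive role to mITT, and the FDA asked for a sensitivity analysis. A reader might infer that the trial's error rate is inflated. It is not: the false-positive figures belong to the LOCF table alone. Nor does the addendum present LOCF as conservative. This stands, and it limits the harm.

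**A likelihood-based analysis is already planned.** The MMRM in SAP Section 7.4.1 uses every observed weekly WI-NRS and AI-NRS score and gives Week 4 differences. For mITT subjects it covers missing-at-random dropout. This also stands. It does not reach randomised subjects outside mITT, whom the FDA request was meant to bring in.

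**The direction is unknown.** A reader might infer that LOCF favours B244. The documents give one overall dropout rate and no split by arm. Equal dropout gives no null bias and shrinks a true effect; more dropout on B244 biases against it.

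**Missing Week 4 data may be fewer than 16.7%.** That rate refers to completing the study, which runs to Week 8 (Protocol Section 11.6), and one diary entry in the Week 4 window yields a score (SAP Section 6.5.3). Smaller dropout gaps give proportionately smaller bias.

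**The SE is right for what LOCF estimates.** In simulation it matched the LOCF estimator's own sampling SD. It is too small only for the Week 4 difference that the analysis is meant to estimate.

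**Conclusion.** The point holds as a weakness of a sensitivity analysis. The bias needs two conditions together: scores still moving at dropout, and dropout that differs by arm. Under the assumptions above it is about 0.06 to 0.23 points towards B244 for splits from 20% / 15% to 25% / 12.5% and improvements of 1 to 3 points (20% / 15% taken at 2 points), against a planned effect of 0.65. It is about 0.13 against B244 when 10% leave vehicle and 20% leave B244, with a 2-point improvement. With equal dropout the only distortion of the estimate is shrinkage of a true effect to about 0.58. The SE shortfall is roughly 5-10%. The trajectories and arm splits are assumed, so these sizes are illustrations, not predictions. The primary mITT ANCOVA is untouched; what the plan lacks is a sound all-randomised analysis.

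**What to change.** Issue a revised addendum in which multiple imputation is the missing-data method for the ITT analysis:

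- For WI-NRS and AI-NRS, impute from baseline and the observed weekly averages. For IGA and EASI, which are scored only at clinic visits, use baseline and the observed visit scores.
- Analyse each completed dataset with the planned model and combine by Rubin's rules. Derive responder status from the imputed scores.
- Add a stress test: either imputation of B244 dropouts from the vehicle arm, or a tipping-point analysis. Which of the two is a matter of preference.
- Keep LOCF as a supplementary display.

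Two shell conflicts can be corrected in the same revision. The footnote to Table 14.2.2.5.13 requires a diary score in the week being analysed yet imputes a missing Week 4. The programming note for Table 14.2.2.7.13 names mITT where the list of tables says ITT.

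No new data are needed. The cost is extra programming and a new addendum version, since the present one was signed on 3 and 5 May 2022.
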